4.6 Rationale for the use of Idebenone in PP-MS

As described above (Section 4.3: Mechanism of tissue injury in PP-MS), mitochondrial dysfunction together with aberrant formation of ROS are believed to underlie at least partially the development of progressive CNS tissue destruction in PP-MS. Idebenone has two key modes of action that make it an attractive therapeutic candidate for PP-MS:

- 1) Idebenone enhances the electron flow in the mitochondrial ETC. Specifically, idebenone can substitute for Coenzyme Q₁₀ as an electron carrier and distribute the electrons between the various dehydrogenases and the cytochrome segments of the respiratory chain (*Sugiyama and Fujita 1985, Sugiyama, Fujita et al. 1985, Imada, Fujita et al. 1989, Geromel, Darin et al. 2002*)
- 2) Idebenone functions as an anti-oxidant against membrane damage caused by lipid peroxidation, including lipid peroxidation that occurs in brain mitochondria (*Suno and Nagaoka 1984, Sugiyama, Fujita et al. 1985, Suno and Nagaoka 1989, McDaniel, Neudecker et al. 2005*).

In view of the hypothesized involvement of mitochondrial dysfunction, and particularly the reduced activity of the ETC, idebenone is a rational treatment choice in PP-MS based on its pharmacological properties. Furthermore, idebenone is known to cross the blood-brain barrier (Torii, Yoshida et al. 1985) and is readily taken up by cells, even those with normal Coenzyme Q₁₀ content (Geromel, Darin et al. 2002), making it superior to natural Coenzyme Q₁₀ for treatment of CNS diseases with presumed mitochondrial dysfunction.

There are several secondary effects of idebenone described in the literature, which may be useful from the standpoint of the presumed pathophysiology of PP-MS:

- 3) Animal studies have documented neuroprotective properties of idebenone *in-vitro* in different models of excitotoxicity (by NMDA and kainite-agonists) (Miyamoto and Coyle 1990, Bruno, Battaglia et al. 1994).
- 4) Idebenone induces nerve growth factor expression in animals (Nitta, Murakami et al. 1994), which represented the basis for its presumed neuroprotective effect in Alzheimer's disease (AD) (Gutzmann and Hadler 1998, Gutzmann, Kuhl et al. 2002). However, this beneficial effect on AD is only very mild and perhaps not highly clinically relevant (Thal, Grundman et al. 2003).
- 5) Idebenone has potential CNS anti-inflammatory activity, as it inhibits metabolism of arachidonic acid by cyclooxygenase and lipoxygenase (Civenni, Bezzi et al. 1999).
- 6) Idebenone may substitute for Coenzyme Q₁₀ in non-mitochondrial locations such as in lysosomes, peroxisomes and plasma membranes, protecting these organelles from ROS-associated damage (Geromel, Darin et al. 2002)

Due to its effect as a scavenger of oxygen radicals and facilitating effect on ETC, idebenone has been used extensively with reported success in patients with mitochondrial diseases (Mashima, Hiida et al. 1992, Ikejiri, Mori et al. 1996, Napolitano, Salvetti et al. 2000, Lerman-Sagie, Rustin et al. 2001, Geromel, Darin et al. 2002), although the desired prospective, double blind clinical trials in these patients have not been performed.

Perhaps the best documented and clinically meaningful example of sustained therapeutic benefit of idebenone in neurodegenerative disease is represented by Friedreich's ataxia (FRDA). FRDA is the most common hereditary ataxia inherited as an autosomal recessive GAA expansion in the first intron of the frataxin gene. Frataxin is a nuclear encoded protein, which is exported to the mitochondria. Frataxin plays an important role in the assembly of mitochondrial FE/S clusters that are key components of the ETC. Its decreased expression therefore leads to reduced activity of the ETC, mitochondrial damage with subsequent increased formation of reactive oxygen species (ROS). It was demonstrated that FRDA have reduced ATP biosynthesis, down to 30% of normal. (Lodi 1999). The reduced activity of the ETC in combination with secondary oxidative damage is believed to underlie the development of neurological disability and hypertrophic cardiomyopathy and diabetes, which are characteristic clinical presentations of this disease. Idebenone has been studied extensively in FRDA (Schols, Vorgerd et al. 2001, Artuch, Aracil et al. 2002, Rustin, Rotig et al. 2002, Buyse, Mertens et al. 2003, Mariotti, Solari et al. 2003, Artuch, Aracil et al. 2004, Rustin, Bonnet et al. 2004, Di Prospero, Baker et al. 2007, Pineda, Arpa et al. 2008), including very successful studies performed at intramural NIH by the Neurogenetics Branch research group under the leadership of [name] (Di Prospero, Baker et al. 2007) in collaboration with Santhera. This study demonstrated that intermediate to high (10-50mg/kg) doses of idebenone were effective in slowing the progression of disability in FA patients as compared to low dose

idebenone (4-8mg/kg) and placebo. Because previous trials using lower doses of idebenone in FRDA demonstrated a positive effect on cardiac function but not on neurological function (*Mariotti, Solari et al. 2003*), it is likely that higher doses of idebenone are necessary for penetration into the CNS.

In conclusion, the three major effects of idebenone (facilitating ETC mitochondrial function, antioxidant/scavenger of ROS and potentially also anti-inflammatory) make it an excellent candidate agent for the treatment of PP-MS based on the neurodegenerative hypothesis described above. Additionally, idebenone is an oral therapy with extensive safety and tolerability data.

4.7 Rationale for current study design

The clinical experience with use of antioxidants in MS is very limited: although a few trials of antioxidants in MS have been reported (*Jensen and Clausen 1986, Spitsin, Hooper et al. 2001, Yadav, Marracci et al. 2005*), all have been small studies of short duration and offered only very limited insight on clinical efficacy (*Spitsin, Hooper et al. 2001*).

Based on this background information, we propose to use idebenone in a proof-of-principle placebo-controlled cross-over Phase I/II clinical trial for PP-MS (Figure 1). Because there are no other therapeutic options for PP-MS, a placebo arm is both ethically justifiable and important to ensure an unbiased evaluation of MRI, clinical and immunological outcome measures. 1:1 randomization between active treatment and placebo will optimize statistical power for detecting differences in the outcome measures.

4.7.1 Figure 1

Idebenone in PP-MS clinical trial design

[figure not shown]

Figure 1: At least one year of pre-treatment baseline will be followed by 1:1 randomization to placebo and idebenone

750mg tid for 2 years. All outcome measures will be collected every 6-12 months as indicated.

There has not been a single successful therapeutic trial in PP-MS thus far and it has become obvious that outcome measures widely used in RR-MS trials are not suitable for PP-MS cohorts. Specifically, reliance on CEL as an outcome measure that allowed rapid screening of promising therapeutic agents in phase II trials of RR-MS patients is not possible in PP-MS, because these patients have a paucity of CEL and the frequency of CEL does not correlate with the development of clinical disability. However, current measurements of clinical disability are too insensitive to detect disease progression in individual PP-MS patients within 2-3 year time frame. As a consequence, promising agents for PP-MS have been tested so far in large, multi-center phase II/III trials, which are prohibitively expensive. Therefore, there is a great need to develop more sensitive measures of CNS tissue destruction that could be utilized as outcomes for smaller phase II trials in PP-MS. Currently the only measure that may theoretically fulfill this need is the individualized rate of development of brain atrophy as measured by SIENA methodology. However, it is highly probable that several newer measures of CNS tissue destruction, such as a decrease in the NAA/Cr ratio measured by MRS or quantitative T1 relaxation time, may be more sensitive than brain atrophy. The reason for this is that irreversible neuronal dysfunction may occur before the development of brain atrophy and that reactive gliosis, which is evident in the pathology of PP-MS, may to a large extent compensate volumetrically for the tissue loss associated with demyelination and neuronal drop-out. However, there are currently no available longitudinal measurements of these biomarkers to allow sample size estimates.

The possible solutions for this problem are twofold: We could perform a natural history study on PP-MS patients, collect longitudinal data and based on their analysis, design a new therapeutic trial of idebenone in the PP-MS population. However, this approach would pose significant delay for the therapeutic part of the trial and would also complicate recruitment efforts: even though none of the current disease modifying therapies (DMT) used in MS proved their efficacy in PP-MS, the relentless progression of neurological disability drives many PP-MS patients and their physicians to try unproved therapies. The second solution is to collect longitudinal data on PP-MS patients just before randomization to the treatment phase of the protocol. There are several advantages to this approach:

- 1) Because the longitudinal baseline (pre-randomization) data can be analyzed while patients proceed to the treatment phase, the administration of treatment does not have to be delayed until all patients complete pre-treatment baseline.
- 2) The NDU “natural history protocol” 09-N-0032, where patients with suspected MS undergo diagnostic work-up, explores the feasibility and utility of the proposed outcome measures. Hence, patients evaluated under this protocol with a final diagnosis of PP-MS can easily proceed to the therapeutic protocol, if so desired, and the data collected at NIB during the diagnostic work-up can be utilized as baseline (pre-randomization) data for the current therapeutic protocol. Historically, the baseline data have also been collected under NIB protocol 89-N-0045.
- 3) Finally, evidence indicates that the rate of CNS tissue destruction differs significantly among individual PP-MS patients, but remains intra-individually relatively stable (i.e. linear) during a 3-5 year follow-up (Ingle, Stevenson et al. 2003). Therefore, collecting 1 year of pre-treatment data on all patients in the therapeutic trial will allow us to calculate individualized rates of CNS tissue destruction and assess the therapeutic effect

of idebenone in relationship to these individualized rates of CNS tissue destruction. This is expected to increase the power of the trial to detect therapeutic effect (see below) without the need to stratify randomization of patients based on the rate of CNS tissue destruction, which is not feasible from the practical standpoint.

Based on this background, we propose to use an adaptive trial design: We will employ a pre-treatment baseline period of at least 12 months, where MRI, clinical and biomarker measurements will be collected in all patients for dual purpose:

[figure not shown]
- 1) To obtain longitudinal quantitative MRI, clinical and electrophysiological data in untreated PP-MS patients before randomization that will be utilized for the selection of the most sensitive primary outcome measure. This will be done on the first 30 patients and subsequent analysis will be used for selection of the most sensitive primary outcome measure and for adjusting sample size calculation (see sample size calculation, Section 11) if the primary outcome measure is different than brain atrophy measured by SIENA methodology and
- 2) To obtain patient-specific pre-randomization baseline for all collected outcome measures, which is expected to increase the statistical power of randomized trials with continuous outcome measures (*Murray, Barer et al. 2005, Young, Lees et al. 2005, Frost, Kenward et al. 2008*). This is because previous longitudinal studies in PP-MS demonstrated that although there is extensive inter-individual variability in the rate of CNS tissue destruction, intra-individually, these rates are relatively stable within 3-5 year follow-up periods (*Ingle, Stevenson et al. 2002, Ingle, Stevenson et al. 2003, Stevenson, Ingle et al. 2004*). In other words: the longitudinal data for the exact MRI, clinical and electrophysiological biomarkers of CNS tissue destruction and clinical disability that we propose to collect in this trial are not available. However, based on published longitudinal studies using analogous, but presumably less sensitive biomarkers of CNS tissue destruction (e.g. ventricular atrophy, cross-sectional cervical spinal cord atrophy collected at 1.5T MRI etc (*Ingle, Stevenson et al. 2003*)) we make two assumptions (Figure 2A): 1. CNS tissue destruction develops in a linear manner within a 3-5 year time-frame in the majority of PP-MS patients and 2. The slopes of the linear development of CNS tissue destruction differ among individual patients. Based on these two assumptions, our trial design will allow adjustment for the individualized rates of development of CNS tissue destruction (Figure 2B), which is expected to increase our power to detect treatment relevant differences between placebo and active therapy groups (*Murray, Barer et al. 2005, Young, Lees et al. 2005, Frost, Kenward et al. 2008*).

The details of analyses of pre-randomization data on the first 30 subjects and the methods for selection of the most sensitive outcome measure are described in detail in Section 11, under Statistical Analyses.

Both active drug and placebo will be supplied by Santhera Pharmaceuticals.

We will use a 2250 mg/day dose (5x150mg tablets three times per day). This dose was well tolerated in Phase I trials in adult patients (*Bodmer, Vankan et al. 2009*) and ensures that each treated patient will receive 10-50mg/kg of idebenone per day, which represents the estimated dose required for CNS efficacy (*Di Prospero, Baker et al. 2007*).

Figure 2
Efficacy measures adjusted for individualized rates of development of CNS tissue destruction in PP-MS

Because this is a pilot study testing a novel mechanism of action (i.e. neuroprotection) in PP-MS with a very limited patient cohort, we need to optimize the trial design and select a patient population that is most likely to benefit from neuroprotective therapy in PP-MS. Specifically, we need to employ a patient population in which neuroprotection and repair are still feasible. Epidemiological data indicate that the major determinant of relentless progression of disability is a patient's age, and not necessarily disease duration (*Confavreux and Vukusic 2006*). This may be due to the fact that natural repair mechanisms, including CNS plasticity and remyelination, decrease with aging (*Crutcher 2002, Confavreux and Vukusic 2006*). It is likely that these natural

repair mechanisms are necessary for achieving effective neuroprotection. Furthermore, the aging process is characterized by decreased ECT function and accumulation of mitochondrial DNA mutations (*Lenaz, Bovina et al. 2002*), which may complicate the differentiation between PP-MS-associated and aging-related mitochondrial dysfunction. The implementation of an upper age limit will eliminate these confounding factors. Because PP-MS is usually diagnosed in the early/late forties, we will limit the age of enrollment in this trial to 65. Setting an age limit will minimize the contribution of aging to the development of CNS atrophy and will ensure that aging will not limit CNS repair mechanisms. In contrast, we will not limit the disease duration. Because the most important outcome measures are neuro-imaging measures and those clinical/functional measures that are not necessarily skewed toward ambulation, we will include patients with moderate disability, up to EDSS 7.0 (i.e. patients who can ambulate with bilateral assistance). We will exclude non-ambulatory patients because of difficulties they would experience with prolonged MRIs, which are necessary for this protocol.

As such, the trial design is Phase I/II, double-blind, placebo controlled, baseline versus treatment with 2 parallel study groups of idebenone versus placebo (Figure 1).

Because of the paucity of suitable outcome measures for Phase II neuroprotective trials in MS, we will use/develop and validate several novel outcome measures in clinical, neuroimaging and immunological categories.

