Specifically, we will analyze MRI and clinical/paraclinical quantitative data when 30 patients reach month 0 (i.e. will complete pre-randomization baseline period)(Kosa, Ghazali et al. 2016). From this analysis we will calculate the rate of progression of CNS tissue destruction as assessed by MRI and clinical biomarkers defined in Section 10.2, for individual patients and for the entire cohort. Because SIENA methodology for detection of progression of brain atrophy, which is currently utilized as the default primary outcome measure, calculates progression of brain atrophy as a %-age of baseline brain tissue, we will perform the same type of analysis for every other defined outcome; i.e. we will quantify the biomarker at month -12 (baseline) and months -6 and 0 and will express the values measured at months -6 and 0 as a %-age of the baseline value (i.e. assigning 100% to the value measured at month -12). For the 1st level of analysis, we will compare all outcome measures based on the measurements collected at month 0 (see Figure 4A for explanation). For each biomarker (i.e. outcome measure) we will calculate the z-score as the average change from baseline divided by the standard deviation (SD). Biomarkers with the most robust change from baseline and lowest spread of values will have the highest z-score. Figure 4A shows 3 hypothetical biomarkers: Biomarker 1 has on average the lowest magnitude of change from baseline (i.e. low sensitivity) and relatively high spread (i.e. low accuracy), leading to the lowest z-score. Biomarker 2 has the most robust change from baseline (i.e. high sensitivity), but also the widest spread of values (i.e. lowest accuracy), resulting in low z-score. Biomarker 3 has an intermediate change from baseline (i.e. intermediate sensitivity) but very low spread of values (i.e. high accuracy), resulting in the highest z-score. Biomarker 3 would be selected as the primary outcome measure.

[figure not shown]

Figure 4:

A/ First level of comparative analysis: all outcome measures will be expressed as %-age of baseline values for all 30 patients. We will calculate z-scores for all outcome measures as Average (30 changes from baseline)/SD and select the biomarker with largest z-score as primary outcome measure.

B/ Second level of comparative analysis: if two biomarkers had identical or very similar z-scores in the first level of analysis, we would evaluate z-scores based on data collected at -6 months using identical methodology.

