This analysis was performed and published, including measurements of z-scores (*Kosa, Ghazali et al. 2016*). We have compared total of 58 clinical, imaging, electrophysiological and optical coherence tomography outcomes. In the first IPPOMS cohort (which ended up being 35 patients because we lost some MRI outcomes due to technical issues such as poor quality of scans and the protocol stipulated minimum of 30 patients per outcome) we observed that total of 15 outcomes reached statistical significance based on un-adjusted p-values (See Table 2 in the (*Kosa, Ghazali et al. 2016*)). We then validated these 15 outcomes for their ability to reliably detect yearly MS disease progression in 2 independent validation cohorts: IPPOMS2 cohort (n=34) and RIVITALISE cohort (n=29). Seven out of 15 outcomes validated statistically-significant change in both independent validation cohorts, when properly adjusting for multiple comparisons. Surprisingly, the default primary outcome for IPPOMS protocol, brain atrophy measured by SIENA methodology was not validated. While six MRI biomarkers (ventricular volume and 5 diffusion-tensor imaging [DTI] markers) validated statistically-significant change in both validation cohorts, our enthusiasm for these outcomes was lowered by observation that only one of them, ventricular atrophy, showed any correlation with clinical outcomes. This measure had mild correlation with 2 cognitive scales (PASAT and SDMT) and with a MS functional composite (MSFC) scale. However, this correlation was observed only in the cross-sectional paradigm, which benefited from a broad range of disabilities present in merged untreated progressive MS cohort (n=98). In contrast, we observed absolutely no correlation between any MRI outcome and any clinical measure in 1-year longitudinal paradigm – in other words, change on MRI biomarkers did not correlate with change in any clinical outcome. The article explains in length why this is so, documenting poor signal-to-noise ratio (SNR) of even best performing MRI biomarkers for the level of change observed in the 1-year longitudinal MS data in comparison to scan-re-scan variability observed in MRI technical controls (i.e. healthy donors scanned twice at each scanner).

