Because of this we concluded that MRI outcomes utilized in small Phase II trial will be unlikely to predict change on clinical outcome (used for Phase III trial), which is a definition of a “surrogacy”. Therefore, we sought alternative outcome. We noticed that clinical scales were much better correlated, even though they too had relatively low SNR. One way to decrease the noise of the measurement is to use repeated measure analysis. Therefore, we hypothesized that to the degree to

which clinical scales reflect overlapping biology (i.e. measure overlapping neurological disability) to that degree they represent repeated measure analysis. Thus, rationally combining clinical scales would allow us to differentiate between disability caused by a structural lesion (which would affect multiple clinical scales congruently) from the performance noise, which would have random distribution among clinical scales. We have tested this hypothesis by designing Combinatorial Weight-Adjusted Neurological Clinical Scale (CombiWISE version 1), where we selected contributing clinical scales and adjusted their “weights” in final formula proportionally to z-scores (defined in the IPPOMS protocol and measured in the first [IPPOMS1] cohort). After we validated that CombiWISE v1 outperforms all other clinical and MRI biomarkers, we used statistical learning based on random permutations of the modeling cohort, to mathematically optimize CombiWISE outcome (Kosa, Ghazali et al. 2016).

Not only mathematically-optimized CombiWISE outperformed all remaining 57 studied outcomes, but it also retained highly statistically significant correlations with majority of clinical outcomes, including EDSS that is currently used for regulatory approval of MS drugs. However, in comparison to EDSS, which is ordinal scale from 0-10, CombiWISE is a continuous scale from 0-100. One point change in EDSS corresponds on average to 7.50 point change in CombiWISE with a standard error of 0.10, making CombiWISE significantly more sensitive (and specific) measure of neurological disability (Kosa, Ghazali et al. 2016).

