11.7 New power analysis

If the above-described analysis of secondary outcome measures identifies a new primary outcome, we will conduct a new power analysis for the selected new primary outcome, using two-sample t-test with estimates of mean and standard deviation of changes from baseline collected on the first 30 enrolled patients. Based on this new power analysis, we will amend the protocol to indicate the final accrual number request.

The new power analysis for CombiWISE, EDSS and ventricular volume change has been published for both within-group and between-group designs (Kosa, Ghazali et al. 2016). Using absolute change in the CombiWISE AUC outcome determined from the pre-treatment baseline data in IPPOMS cohort, following power calculation for AUC was derived:

Drug effect	untreated	treated	difference	Actual Power	N Pairs	Distribution	Normal
50%	51.24	25.62	25.62	0.807	28	Method	Exact
45%	51.24	28.18	23.06	0.806	34	Number of Sides	2
40%	51.24	30.75	20.50	0.802	42	Standard Deviation	46.2
35%	51.24	33.31	17.94	0.807	55	Correlation	0.5

30%	51.24	35.87	15.37	0.801	73	Nominal Power	0.8
25%	51.24	38.43	12.81	0.804	105	Null Difference	0
20%	51.24	40.99	10.25	0.802	162	Alpha	0.05

This demonstrates that substituting default primary outcome (Brain atrophy measured by SIENA (*Altmann, Jasperse et al. 2008*)) with CombiWISE primary outcome will significantly enhance power of the IPPoMS trial from estimated 80% of power to detect at least 50% drug effect to more than 80% power to detect at least 40% drug effect. Additionally, while brain atrophy measured by SIENA does not correlate with clinical outcomes, CombiWISE has strong, highly significant correlations with EDSS, which is used for regulatory approval of MS treatments, both in cross-sectional and longitudinal paradigms (i.e. yearly change in CombiWISE correlated with yearly change in EDSS). Therefore, CombiWISE can predict efficacy on EDSS outcome, but does so in considerably smaller cohorts and/or trials of shorter duration (*Kosa, Ghazali et al. 2016*).

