6.2 New sample size calculation

In 2016, a pre-determined analysis of the 58 outcome measures collected in 1 year pre-treatment baseline period on first ≥ 30 IPPOMS patients was performed and published and validated these findings with the 2 validation cohorts consisting of 34 remaining IPPOMS patients and 29 SP-MS patients from RIVITALISE trial (Kosa, Ghazali et al. 2016). This analysis demonstrated that above-stated assumptions or the original sample size calculation were incorrect, that brain atrophy measured by SIENA technology was not more sensitive than clinical outcomes. Instead, based on this pre-defined analysis we selected CombiWISE as primary outcome and brain ventricular atrophy measured by LesionTOADS methodology as secondary outcome.

Up to 85 subjects are planned to be recruited based on current sample size calculation, to account for 20% drop-out and final number of treated subjects 33 per arm (66 total). These recruitment numbers were already achieved and interim analysis of the blinded data of the outcomes showed enhanced, rather than diminished power of new primary outcome (CombiWISE) in comparison to original default primary outcome (Brain atrophy measured by SIENA).

The new power analysis for CombiWISE, EDSS and ventricular volume change has been published for both within-group and between-group designs (Kosa, Ghazali et al. 2016). Using absolute change in the CombiWISE AUC outcome determined from the pre-treatment baseline data in IPPOMS cohort, following power calculation for AUC was derived:

Drug effect	CombiWISE AUC (untreated)	CombiWISE AUC (treated)	CombiWISE AUC (difference)	Actual Power	N Pairs	Distribution	Normal
50%	51.24	25.62	25.62	80.7	28	Method	Exact
45%	51.24	28.18	23.06	80.6	34	Number of Sides	2
40%	51.24	30.75	20.50	80.2	42	Standard Deviation	46.2
35%	51.24	33.31	17.94	80.7	55	Correlation	0.5
30%	51.24	35.87	15.37	80.1	73	Nominal Power	0.8
25%	51.24	38.43	12.81	80.4	105	Null Difference	0
20%	51.24	40.99	10.25	80.2	162	Alpha	0.05

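### The CombiWISE power table takes its mean and SD at least partly from the patients used to choose and weight the score, so its planning ratio is expected to be optimistic, by an amount the documents do not fix.

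*Protocol*

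**What the plan says.** **Plan.** Protocol 4.7 uses the pre-treatment data of the first 30 patients for two purposes: "subsequent analysis will be used for selection of the most sensitive primary outcome measure and for adjusting sample size calculation". Section 11.5 defines a z-score for each outcome (average change from month -12 divided by its SD, values expressed as a percentage of month -12, compared at month 0). Its Figure 4 legend gives the rule: "select the biomarker with largest z-score as primary outcome measure". Section 11.7 then plans a new power analysis "using two-sample t-test with estimates of mean and standard deviation of changes from baseline collected on the first 30 enrolled patients".

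**Execution.** Section 11.5 reports: "We have compared total of 58 clinical, imaging, electrophysiological and optical coherence tomography outcomes". The first cohort, IPPOMS1, had 35 patients. IPPOMS2 (34 patients) and RIVITALISE (29 SP-MS patients) served for validation. The weights of CombiWISE version 1 were set "proportionally to z-scores (defined in the IPPOMS protocol and measured in the first [IPPOMS1] cohort". After version 1 had been validated, the score was refined by a statistical-learning step on a modelling cohort whose membership is not given.

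**Planning values.** Protocol 11.7 and SAP 6.2 carry the same power table, introduced with "Using absolute change in the CombiWISE AUC outcome determined from the pre-treatment baseline data in IPPOMS cohort". Neither document says that IPPOMS1 was left out. Neither describes a held-out, cross-validated or shrunken estimate of the mean or SD.

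**The concern.** At a fixed number of patients and a fixed correlation, the power in this table depends only on the drug effect multiplied by mean/SD. A ratio of the same type was the criterion for choosing the outcome and for weighting its components. When the same patients choose or tune a measure for a high mean/SD and then supply the mean and SD for planning, chance variation that favoured the measure is carried into the power calculation.

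What is at stake is the statement in Protocol 11.7 and SAP 6 that the switch to CombiWISE gives the trial over 80% power for a 40% drug effect. A reader who accepts it will treat a null result as stronger evidence against an effect of that size than it is. Protocol 7.6.10 now records that no significant efficacy was found, so the point is practical.

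**Working it through.** **Inputs** (Protocol 11.7, SAP 6.2): untreated mean AUC 51.24; SD 46.2; correlation 0.5; two-sided alpha 0.05; paired design.

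**1. Reproduce the table.** SD of the paired difference = 46.2 × √(2 × (1 − 0.5)) = 46.2. Planning ratio R = 51.24/46.2 = 1.109. Power comes from the noncentral t distribution with n − 1 degrees of freedom and noncentrality e × R × √n, where e is the drug effect. For the 40% row: 0.40 × 1.109 × √42 = 2.875, giving 80.2%. All seven rows reproduce in N (28, 34, 42, 55, 73, 105, 162) and, to within 0.001, in power.

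**2. Lower the ratio** (assumed reductions; 40% effect).

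| True ratio lower by | R | Power at 42 pairs | Pairs for 80% |
|---|---|---|---|
| 0% | 1.109 | 80.2% | 42 |
| 5% | 1.054 | 76.0% | 47 |
| 10% | 0.998 | 71.5% | 52 |
| 20% | 0.887 | 61.3% | 65 |

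**3. How large might the optimism be?** The documents give no CombiWISE AUC mean or SD from patients outside the tuning, so this can only be illustrated.

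- Weights proportional to component z-scores, as described for version 1: with 4 or 6 components, true component z-scores of 0.3 to 1.0 and correlations of 0 to 0.6, simulation gives true/observed of about 0.89 to 0.96 when the same 35 patients tune and plan. It is 0.94 to 0.98 when 35 tune and 69 (35 + 34) plan. Other assumptions take it down to about 0.76.
- Fully optimal weights give about 0.50 to 0.92. That is harsher than the weighting described for version 1. The later optimisation may lie nearer to it, but the documents do not say.

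**4. The trial's own comparison.** The primary analysis compares two arms of 33. For a two-sample test the noncentrality is e × R × √(33/2), with 64 degrees of freedom. For a 40% effect: 0.40 × 1.109 × 4.062 = 1.802, giving 42.7% at the stated ratio. Ratios 5%, 10% and 20% lower give 39.2%, 35.9% and 29.5%. If the covariates achieve the table's correlation of 0.5, the SD falls by the factor √(1 − 0.25), and ANCOVA power at the stated ratio is 53.6%. The optimism thus passes through either formula, but the paired basis costs more than any reduction shown in step 2.

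**The case against.** - **CombiWISE was validated in two other cohorts.** This supports it as an outcome. It does not replace the planning mean and SD, and the final optimisation came after version 1 was validated.
- **Mean/SD of the AUC was not what was maximised.** This stands. Selection used percentage change at month 0, while the table uses absolute change in AUC. The objective and the patients of the final optimisation are not stated, and it used random permutations of unknown effect. A reader might infer that 1.109 is an in-sample maximum, or size the bias as for the best of 58 z-scores in 30 patients. The documents support neither. CombiWISE was constructed, not just picked from a list, and the overlap may be partial if the IPPOMS cohort means all 69 patients.
- **The ratio is a one-year value and the endpoint covers two years.** This stands as a limit. In the documents' own table for brain atrophy in SP-MS, the number per arm for a 50% effect at 80% power falls from 57 to 33 between one and two years. That implies a ratio higher by √(57/33) = 1.31, enough to offset about 24% optimism (1 − 1/1.31). It is a different outcome and population, so it shows only that the net direction for two-year power is open.
- **The values set no enrolment number.** This stands. The target of 66 treated patients came from the published SP-MS table, and recruitment was complete.
- **The claim of enhanced power has another source.** SAP 6.2 attributes it to an interim look at blinded data and does not tie it expressly to this table. The statement of over 80% power for a 40% effect does follow from the table.

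**Conclusion.** The point holds in a limited form. Selection, first-stage weighting and planning draw on overlapping pre-treatment patients, and nothing corrects for it, so the planning ratio of 1.109 is at least partly in-sample and expected to be optimistic. The mechanism is clear from the documents; the size is not. The falls to 76.0%, 71.5% and 61.3% illustrate assumed reductions and are not estimates.

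Only the stated power is affected. A reader might infer that the trial was under-recruited because of this, or that its test is invalid. Neither follows: the accrual target has another source, and selection used pre-randomisation data, so the type I error of the between-arm test is untouched. The paired basis of the table is a separate and larger fault: about 43% two-sample power for a 40% effect at 33 per arm, even with the ratio as stated. Correcting the inputs alone would not rescue the claim. The trial's null result should be read from its confidence interval, not from the planning statement.

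**What to change.** In Protocol 11.7 and SAP 6.2:

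1. Label the present table as partly in-sample.
2. State which patients formed the modelling cohort and which supplied 51.24 and 46.2.
3. Recompute the CombiWISE AUC mean and SD with the frozen formula in IPPOMS2, if that cohort was held out of the final optimisation. Otherwise use a cross-validated or shrunken estimate. Show RIVITALISE as supportive only, because it is SP-MS.
4. Restate power and detectable effect over a range of ratios for the between-arm ANCOVA with 33 per arm, and withdraw or reword the claim of over 80% power for a 40% effect.

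Two tempting remedies should be avoided. The blinded two-year data of 50 patients (Protocol 11.2) are not an out-of-sample source: at least 50 − 34 = 16 of them must come from outside IPPOMS2, and they pool both arms. Section 4.7 should not be rewritten to say that different patients were used, because that would misdescribe the rule as carried out.

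The cost is one recalculation on data already in hand and some wording. No further patients are needed. The downside is a less favourable stated power.
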